#### **6.7.3.4. *Time to signs/symptoms of GCA or new or worsening vasculitis by imaging by week 26***

Time to signs/symptoms of GCA or new or worsening vasculitis by imaging will be defined as the time from randomization to earliest date of subjects experiencing signs/symptoms of GCA, or new or worsening vasculitis by imaging. All subjects who do not have an event by week 26/ EOT will be censored at last assessment date and/or randomization date, whichever is later. Detailed censoring rule follows that for ESR.

Analysis and presentation will be the same as that of the primary efficacy endpoint. The KM method to estimate the survival functions for each treatment group (overall and by stratification factor). The treatment comparison will be based on a stratified log-rank test. The HR and its 95% CI will be estimated using a stratified Cox model with treatment as the explanatory variable and strata as the stratification factor.

#### **6.7.3.5. *Cumulative steroid dose at Week 26 and at the End of the Washout Safety Follow-up Period***

The cumulative corticosteroid dose from first dose date of study drug to Week 26 will be compared between the treatment descriptively, and analytically using analysis of covariance (ANCOVA). The stratification factor and the corticosteroid starting dose will be the covariates in the model for treatment comparisons. The analyses will include 95% CIs for the difference of the mean cumulative steroid doses between the treatment groups.

Similar analysis will be conducted for cumulative steroid dose from first dose date to the end of the washout safety follow up period.

The average daily dose during the same periods will be summarized descriptively.

#### **6.7.3.6. *Percentage of subjects who have completed the corticosteroid taper and who have a normal ESR by week 26***

The number and percentage of subjects who completed the corticosteroid taper per schedule and have normal ESR ( $< 30$  mm/hr) by week 26 will be presented by treatment. Subjects will be considered to have completed the corticosteroid taper if receiving 1 mg/day for those start at 60 mg/day starting dose, or 0 mg/day for those start with doses less than 60 mg/day by week 26 and maintain through week 26. Having normal ESR by week 26 requires all assessments of ESR from the completion of corticosteroid taper through week 26 being normal. If there is no assessment after completion of taper, the subject will not be counted in the numerator.

The percentage will be compared between the treatment groups using a Cochran-Mantel-Haenszel test controlling for the stratification factor; the 95% confidence interval for the difference of percentages will be displayed using the Mantel-Haenszel weight for the stratification factor.

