Subjects who experience a flare or subjects who cannot adhere to the protocol-defined steroid taper due to a flare should be managed to ensure the best possible care of the subject. The subject must discontinue the assigned study drug (KPL-301 or placebo) and should receive escape therapy in accordance with local SoC, which may include, for example, dose modifications of corticosteroids, other immunomodulatory agents, and/or approved therapies (e.g. tocilizumab). Escape corticosteroid therapy can be escalated immediately. Due to possible safety and pharmacologic effects resulting from overlapping exposures to immunomodulatory agents on top of coadministered corticosteroids, the investigator should consider a washout period of at least 35 days (based on elimination half-lives) after the last dose of study drug if deemed clinically appropriate. The dosages of all concomitant medications used to treat the GCA flare must be entered into the eCRF.

Any subject who prematurely discontinues the study drug treatment for safety or other reason will have an EOT visit and will be followed for the intended duration of study treatment (i.e., through Week 26 and Washout Safety Follow-up) to address potential issues of informative censoring. Any subject who withdraws consent from the trial (i.e., all study procedures in addition to study drug) must complete at a minimum the Final Washout Safety Follow-up visit 84 ± 3 days from the last dose administered. Additional follow-up using public records may be captured where possible.

An analysis of the study will be performed when the last subject reaches Week 26 according to the SAP.

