### **1.3. Sample Size Justification**

The sample size calculation was based on the assumption that time to flare follows an exponential distribution and the proportion of subjects without a flare by week 26 will be 50% in placebo and 85% in KPL-301, the median time to flare would be approximately 26 weeks in placebo arm and 111 weeks in KPL-301 arm. The hazard ratio (KPL-301 vs. placebo) would be approximately 0.234. With a 2-sided significance level of 0.05 and a 3:2 randomization ratio for KPL-301 vs. placebo, it would require approximately 20 events to achieve 87% power using a two-sided log rank test.

Approximately 70 subjects will be randomized by disease stratum (new-onset or relapsing/refractory) to receive KPL-301 or placebo at a 3:2 allocation ratio.

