### **5.1.7. Week 26**

Week 26 in this document refers to the completion of the treatment period, which might not be exactly the 26th week, e.g. if due to treatment delay/use of + 3 days of out of window visit allowance more than 2 times. Efficacy assessments before the safety follow up will all be included in “at week 26”, or “by week 26” analyses unless otherwise specified.

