#### **6.7.1. Multiplicity Adjustment**

Multiplicity adjustment with respect to the primary efficacy and secondary efficacy endpoints will be adjusted using the gate-keeping hierarchical testing procedure. The hierarchy order of the secondary endpoints is presented in Section 3.2. For each endpoint, the null hypothesis is that there is no treatment difference between KPL-301 and placebo. The alternative hypothesis is that KPL-301 is superior to placebo. For each test, the 2-sided type I error rate is 0.05. The primary endpoint will be tested first. If the 2-sided p-value is  $\leq 0.05$ , statistical significance of the primary endpoint will be claimed, and the next hierarchical endpoint will be tested. This process will continue until an endpoint is not statistically significant.

There is no adjustment for other endpoints.

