**6.7.3.7. *Percentage of subjects who have completed the corticosteroid taper and who have a normal CRP by week 26***

[figure not shown]
The number and percentage of subjects who complete the corticosteroid taper and have normal C-reactive protein (<1.0 mg/dL) by week 26 will be presented by treatment. Having normal CRP by week 26 requires all assessments of CRP from the completion of corticosteroid taper through week 26 being normal. If there is no assessment after completion of taper, the subject will not be counted in the numerator.

[figure not shown]
[figure not shown]
[figure not shown]
[figure not shown]
The percentage will be compared between the treatment groups using a Cochran-Mantel-Haenszel test controlling for the stratification factor; the 95% confidence interval for the difference of percentages will be displayed using the Mantel-Haenszel weight for the stratification factor.

[figure not shown]
[figure not shown]
**6.7.3.8. *Percentage of subjects who completed the corticosteroid taper and who have no signs/symptoms of GCA or new or worsening vasculitis by imaging by week 26***

The number and percentage of subjects who complete the corticosteroid taper and who have no signs/symptoms of GCA by week 26 will be presented by treatment. Having no signs/symptoms of GCA by week 26 requires all assessments of from the completion of corticosteroid taper through week 26 showing no signs/symptoms of GCA or new or worsening vasculitis by imaging by week 26. If there is no assessment after completion of taper, the subject will not be counted in the numerator.

The percentage will be compared between the treatment groups using a Cochran-Mantel-Haenszel test controlling for the stratification factor; the 95% confidence interval for the difference of percentages will be displayed using the Mantel-Haenszel weight for the stratification factor.

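### The three taper-completion secondaries (SAP 6.7.3.6 to 6.7.3.8) do not make a flare or escape therapy a non-response, so a flare rescued without steroids can be scored as a success

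*SAP*

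**What the plan says.** SAP 6.7.3.6 defines taper completion by dose: 1 mg/day for subjects who started at 60 mg, and "0 mg/day for those start with doses less than 60 mg/day by week 26 and maintain through week 26". ESR must then be normal at every assessment from taper completion through Week 26. SAP 6.7.3.7 and 6.7.3.8 use the same window for CRP and for signs, symptoms and imaging. The only stated reason for removing an otherwise qualifying subject from the numerator is missing data: "If there is no assessment after completion of taper, the subject will not be counted in the numerator". The opening sentence of 6.7.3.6 says the taper was completed 'per schedule'; 6.7.3.7 and 6.7.3.8 do not repeat this.

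Protocol 8.4.1 requires study drug to stop at flare and allows escape therapy that includes "other immunomodulatory agents, and/or approved therapies (e.g. tocilizumab"). Protocol 10.3 says the same. Subjects who stop study drug are followed through Week 26 and keep attending scheduled visits (Protocol 8.4.1 and the Table 1 footnotes). SAP 5.1.7 adds "Efficacy assessments before the safety follow up will all be included in" the Week 26 analyses.

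Other endpoints handle flare differently. Sustained remission (SAP 6.7.3.1) requires no flare. The time-to-event endpoints are censored at early end of treatment (SAP Tables 1 and 2). No such rule is given for the three percentages.

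**The concern.** A responder endpoint that combines taper completion with normal findings will be read as disease controlled, off or nearly off steroids, on the assigned treatment. As written, a control achieved by the escape drug can be credited to the randomised arm. The same subject can then be a failure on the primary endpoint and the first secondary, and a success on secondaries six, seven and eight.

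More flares are expected on placebo, so such successes would fall mainly there and pull the arms together. These endpoints are in the formal hierarchy (SAP 3.2 and 6.7.1). A diluted, non-significant result on one of them stops testing of those that follow, the last of which is cumulative steroid dose at the end of washout.

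**Working it through.** **Inputs.** SAP 1.3: "the proportion of subjects without a flare by week 26 will be 50% in placebo and 85% in KPL-301"; "The hazard ratio (KPL-301 vs. placebo) would be approximately 0.234"; "it would require approximately 20 events to achieve 87% power using a two-sided log rank test". SAP 6.7.1: "For each test, the 2-sided type I error rate is 0.05". Protocol 8.6: 42 KPL-301 and 28 placebo subjects. Protocol Table 3: taper weeks by starting dose.

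**1. The plan's own figure.** HR = ln(0.85)/ln(0.50) = 0.2345. Freedman's formula with allocation 1.5:1 and 20 events gives z = √(20 × 1.5) × (1 − 0.2345)/(1 + 1.5 × 0.2345) = 3.10, and power = Φ(3.10 − 1.96) = 87.3%. Schoenfeld's formula gives 88.8%. The stated 87% is reproduced. Expected flares are 28 × 0.50 = 14 on placebo and 42 × 0.15 = 6.3 on KPL-301, 20.3 in all, in line with the 20 events.

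**2. One subject traced through the rules.** Take a placebo subject who starts at 30 mg, flares at Week 6 (adjudicated), stops study drug and receives a non-steroid escape agent, while prednisone follows Table 3. The last 1 mg dose falls in Week 22, so the dose is 0 mg from Week 23.

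| Endpoint | Result |
|---|---|
| Time to flare | Event at Week 6 |
| Sustained remission | Not achieved |
| Taper completed (6.7.3.6) | Yes; also 'per schedule' |
| ESR, CRP, signs/imaging, judged over Weeks 23 to 26 | Success on all three if normal; the scheduled visits in the window are Weeks 24 and 26 |

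**3. A flare after taper completion.** A subject at 0 mg from Week 23 who flares at Week 25 on CRP with a normal ESR would meet the ESR endpoint only if no steroid were restarted before Week 26. A restart breaks the requirement to maintain the dose.

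**4. Dilution.** Let a share f of flared subjects in each arm be scored as successes. The success rate rises by 50f points on placebo and 15f points on KPL-301, so the difference shrinks by (50 − 15)f = 35f points. For f = 10%, 20% and 30% (assumed) this is 3.5, 7.0 and 10.5 points. One such placebo subject adds 1/28 = 3.6 points to the placebo rate. If f differs by arm, the difference still shrinks unless the KPL-301 share exceeds 50/15 = 3.3 times the placebo share.

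**5. Power, for illustration.** Assume every flare-free subject succeeds, and ignore the strata. Power = Φ((d − 1.96 SE₀)/SE₁), with SE₀ pooled and SE₁ unpooled. At f = 0 this is Φ((0.350 − 1.96 × 0.1107)/0.1094) = 88.8%.

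| f (assumed) | Placebo | KPL-301 | Difference (points) | Power | Exact check |
|---|---|---|---|---|---|
| 0 | 50.0% | 85.0% | 35.0 | 88.8% | 88.9% |
| 10% | 55.0% | 86.5% | 31.5 | 83.5% | 84.3% |
| 25% | 62.5% | 88.75% | 26.25 | 73.5% | 75.8% |

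The exact column enumerates the unstratified Mantel-Haenszel chi-square. If only 90% of flare-free subjects succeed, approximate power is 77.2% at f = 0 and 53.9% at f = 25%. The SAP states no power for these endpoints.

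**The case against.** The best defence is that completing the taper already means completing the protocol taper. SAP 6.7.3.6 says 'per schedule', and its split between 1 mg and 0 mg matches where Table 3 leaves each starting dose. Protocol section 9 separates the taper from escape therapy, and SAP 6.6.5 summarises cumulative taper dose only to the earlier of flare and Week 26. SAP 6.7.3.7 and 6.7.3.8 contain no definition of their own, so they should inherit 6.7.3.6 with its qualifier.

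This carries weight for steroid rescue. A reader might infer that every rescued subject who later reaches 0 mg counts as a success. The documents do not establish that, because a subject whose prednisone was raised above Table 3 may fail 'per schedule'. But the phrase governs prednisone dose. It does not reach the subject in step 2, whose prednisone stays on Table 3 and whose rescue is not a steroid. Nor is the phrase written into the other two subsections.

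A second defence is that SAP 5.1.7 equates Week 26 with completion of the treatment period, which for a flared subject could mean early end of treatment. SAP Table 1 lists the two as separate scenarios, so this reading is not secure. The per-protocol set does not help: it removes only medication changes made before a flare or end of treatment, and the secondary analyses use mITT.

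It is also fair to say that qualifying is hard. The dose must reach 0 or 1 mg/day by Week 26 with all later findings normal, and investigators are asked to consider a 35-day washout after the last dose of study drug. That limits f; it does not make f zero. Finally, flare is already covered by sustained remission, so overlap is a real cost of any change.

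**Conclusion.** The point holds. The stated rules do not treat flare or escape therapy as a non-response in SAP 6.7.3.6 to 6.7.3.8, and a flare rescued without steroids can be scored as a success on all three. The expected effect is dilution of 35f points, resting on the plan's flare rates and an equal f in both arms.

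Three stronger readings should be avoided. The range of 3.5 to 10.5 points is not an estimate, because f is assumed and nothing in the documents supplies it; the power figures also assume that all, or 90%, of flare-free subjects succeed. There is no demonstrated false-positive risk: the gap applies to both arms and, with more placebo flares expected, works against KPL-301. A late flare is not automatically a success on the unaffected marker, since step 3 shows that this needs no steroid restart before Week 26.

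The primary endpoint and the first five secondaries are untouched. The change is worth making because the rule gives a classification at odds with the primary endpoint and is cheap to correct.

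**What to change.** In each of SAP 6.7.3.6, 6.7.3.7 and 6.7.3.8, state that a subject with an adjudicated flare, or any escape therapy, from randomization through Week 26 is a non-responder and stays in the denominator. Adjudication should define flare here because SAP 6.7 makes it primary; repeat the analysis with investigator-assessed flare as supportive. State also that the 6.7.3.6 definition of taper completion, including 'per schedule', applies to 6.7.3.7 and 6.7.3.8. The criteria for ESR, CRP, and signs and imaging can stay as they are.

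The cost is a few sentences. Flare work-up and flare medication already go into the eCRF (Protocol 8.4.1), and escape therapy is already summarised (SAP 6.6.6). Reported success rates would be slightly lower, and the three endpoints would overlap more with sustained remission.

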**6.7.3.7. *Percentage of subjects who have completed the corticosteroid taper and who have a normal CRP by week 26***

[figure not shown]
The number and percentage of subjects who complete the corticosteroid taper and have normal C-reactive protein (<1.0 mg/dL) by week 26 will be presented by treatment. Having normal CRP by week 26 requires all assessments of CRP from the completion of corticosteroid taper through week 26 being normal. If there is no assessment after completion of taper, the subject will not be counted in the numerator.

[figure not shown]
[figure not shown]
[figure not shown]
[figure not shown]
The percentage will be compared between the treatment groups using a Cochran-Mantel-Haenszel test controlling for the stratification factor; the 95% confidence interval for the difference of percentages will be displayed using the Mantel-Haenszel weight for the stratification factor.

[figure not shown]
[figure not shown]
**6.7.3.8. *Percentage of subjects who completed the corticosteroid taper and who have no signs/symptoms of GCA or new or worsening vasculitis by imaging by week 26***

The number and percentage of subjects who complete the corticosteroid taper and who have no signs/symptoms of GCA by week 26 will be presented by treatment. Having no signs/symptoms of GCA by week 26 requires all assessments of from the completion of corticosteroid taper through week 26 showing no signs/symptoms of GCA or new or worsening vasculitis by imaging by week 26. If there is no assessment after completion of taper, the subject will not be counted in the numerator.

The percentage will be compared between the treatment groups using a Cochran-Mantel-Haenszel test controlling for the stratification factor; the 95% confidence interval for the difference of percentages will be displayed using the Mantel-Haenszel weight for the stratification factor.

## **6.8. Safety Analysis**

All safety analyses will be conducted based on the Safety Analysis Set. All safety data including those collected during the Washout Safety Follow-up will be listed by subject.

### **6.8.1. Adverse Events**

An adverse event (AE) is any untoward medical occurrence in a subject or clinical investigation subject administered a pharmaceutical product. An AE does not necessarily have a causal relationship with this treatment. Drug-related AEs will be considered those to be at least possibly related to investigational product based on the investigator's assessment.

Treatment emergent AEs (TEAEs) is defined as AEs that begin after the first administration of investigational products or existing AEs that worsen after the first dose of study medication through the 90 days after the last dose date.

TEAEs will be coded using MedDRA version 21.0. A summary of the frequency (number and percentage of subjects) of TEAEs will be presented by system organ class (SOC) and preferred term (PT) by treatment, in decreasing frequency of SOC and PT in the KPL-301 arm. The TEAE will also be analyzed by their severity (mild, moderate or severe), relationship to study drug, leading to death, resulting in dose interruption, leading to withdrawal of study treatment. Treatment emergent serious AEs (TESAE), drug related TESAEs, TEAE of special interest (TEAESI) will also be tabulated.

An adverse event of special interest (AESI) is one of scientific and medical interest specific to understanding of the Investigational Product and requires close monitoring and rapid communication by the investigator to the sponsor. An AESI may be serious or non-serious. AESI are defined in Section 13.1.3 of the protocol.

A subject experiencing the same AE multiple times will be counted only once for that preferred term. Similarly, if a subject experiences multiple AEs (preferred terms) within the same system organ class, then that subject will be counted only once for that system organ class. When summarizing by severity and relationship, only event with highest severity or relationship will be counted.

Tables will include the following details:

- Overview of TEAEs (summary from all the subsequent tables)
- TEAEs by severity
- Drug related TEAEs
- TESAEs
- Drug related TESAEs
- Non-serious TEAEs
- TEAESI
- TEAEs leading to permanent discontinuation of study drug
- TEAEs leading to dose interruption
- TEAEs resulting in deaths.

All AEs and SAEs occurring throughout the conduct of the study, including all-cause deaths, will be displayed in listings.

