Subjects who experience a flare or subjects who cannot adhere to the protocol-defined steroid taper due to a flare should be managed to ensure the best possible care of the subject:

- The subject must discontinue the assigned study drug (KPL-301 or placebo) and should receive escape therapy in accordance with local SoC, as determined by the Investigator, which may include, for example, dose modifications of corticosteroids, other immunomodulatory agents, and/or approved therapies (e.g., tocilizumab). The dosages of all concomitant medications used to treat the GCA flare must be entered into the eCRF.
- Escape corticosteroid therapy can be escalated immediately. Due to possible safety and pharmacologic effects resulting from overlapping exposures to immunomodulatory agents on top of co-administered corticosteroids, the investigator should consider a washout period of at least 35

days (based on elimination half-lives) after the last dose of study drug if deemed clinically appropriate.

Any subject who prematurely discontinues the study drug treatment for safety or other reason will have an End-of-Treatment (EOT) visit and will be followed for the intended duration of study treatment (i.e., through Week 26 and Washout Safety Follow-up) to address potential issues of informative censoring. Any subject who withdraws consent from the trial (i.e., all study procedures in addition to study drug administration) must complete at a minimum the Final Washout Safety Follow-up visit 84 ± 3 days from the last dose administered. Additional follow up using public records may be captured where possible.

Washout Safety Follow-up:

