Urine pregnancy test		X						X				X	X			X
Hematology	X	X					X	X		X		X	X			X
Chemistry	X	X					X	X		X		X	X			X
Liver profile	X	X					X	X		X		X	X			X
Fasting lipid panel and HbA _{1c}		X										X	X			X
Urinalysis		X										X	X			X

Assessment	Screening	Double – Blind Treatment Period (± 3 days)											UNS ^b	Washout Safety Follow-up (± 3 days)			
	Up to 6 weeks	Baseline/Day 0	Week 1	Week 2	Week 3	Week 4	Week 8	Week 12	Week 16	Week 20	Week 24	Week 26 / EOT ^{ac}		Week 30	Week 34	Final Safety Follow-up ^c / Week 38	
Adverse events	X	X	X	X	X	X	X	X	X	X	X	X	X	X	X	X	X
Concomitant medications	X	X	X	X	X	X	X	X	X	X	X	X	X	X	X	X	X
KPL-301 or PBO administration/dispensing		X ^{dc}		X ^e		X ^e	X ^e	X ^e	X ^e	X ^e	X ^e	X ^e	X ^e				
Prednisone dispensing ^k		X	X	X	X	X	X	X	X	X	X	X	X	X	X	X	

CRP=C-reactive protein; CT=computed tomography; CTA=computed tomography angiography; DLCO= diffusing capacity for carbon monoxide; EOT=end of treatment; ESR= erythrocyte sedimentation rate; GCA= giant cell arteritis; Hb1Ac= haemoglobin A1c (glycolysed haemoglobin); IMP = KPL-301 or placebo; MRI=magnetic resonance imaging; O₂=oxygen; PBO=placebo; PET=positron emission tomography; TB=tuberculosis; UNS=unscheduled visit;

- EOT visit must be conducted in the event the subject permanently discontinues KPL-301 or placebo. After the EOT visit, subjects who discontinue treatment should continue attending their remaining scheduled visits for the duration of the study.
- In the event of an unscheduled visit, only the relevant assessments/activities pertaining to the visit need to be captured. Subjects reporting worsening of GCA symptoms or any safety issues may be brought in for an unscheduled visit at the study clinic at any time. This visit can be combined with the EOT visit in which all necessary EOT related assessments/activities should be completed.
- All subjects, including subjects who prematurely discontinue the study (i.e., withdraw consent), must complete at a minimum the Final Safety Follow up visit 84 ± 3 days after the EOT Visit. Additional follow up using public records may be captured if possible.
- At baseline, subject and/or caregiver should be trained on proper self-administration and handling and accountability of study drug. This training should be documented and can be repeated as necessary throughout the study.

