14.6.1 Adverse Events

Adverse events will be mapped to preferred term (PT) and system organ class (SOC) using the most up to date version of Medical Dictionary for Regulatory Activities (MedDRA). AEs that begin after the first administration of investigational products or existing AEs that worsen after the first dose of study medication are considered treatment emergent AEs (TEAEs). The number and percentage of subjects reporting TEAEs will be summarized for each treatment group by MedDRA SOC and PT, by severity, and by relationship to study treatment. Drug-related AEs will be considered those to be at least possibly related to investigational product based on the investigator's assessment. The number and percentage of subjects with serious AEs, AESI, and the number and percentage of subjects with AEs leading to treatment discontinuation will also be summarized for each treatment group by MedDRA system organ class and preferred term.

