## **5.1. Data Analysis General Information and Definition**

### **5.1.1. Study Drug**

Study drug or study treatment refers to SC KPL-301 or placebo.

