## **7. CHANGES TO PLANNED ANALYSES FROM THE PROTOCOL**

### **7.1. Changes from Protocol**

- The protocol stated the first administration of subcutaneous KPL-301/placebo and oral prednisone taper will take place at the study site on Day 0. In this SAP, we defined the first administration of subcutaneous KPL-301/placebo as Day 1. The start date of the oral prednisone taper is not included the definition of Day 1 since not all patients took the first dose of subcutaneous KPL-301/placebo and oral prednisone taper on the same day.
- TEAE definition was updated to include AE through last dose + 90 days.
- CM definition was updated to include medications through last dose + 90 days.
- Included PFTs, DLCO, Dyspnea score, O2 saturation in safety endpoints.
- The protocol described the categories of cranial symptoms as follows. [Section 6.7.2](#) of this SAP adopts the abbreviated categories from the eCRF.
  - New or recurrent headache or pain or tenderness of the scalp or the temporal artery

- Visual signs/symptoms such as ischemic retinopathy, optic neuropathy, diplopia, amaurosis fugax, etc.
- New or recurrent claudication of the tongue, masseter muscle, or worsening temporal artery signs and symptoms
- Transient ischemic attack (TIA) or stroke related to GCA in the opinion of the Investigator
- The protocol described the categories of extracranial symptoms as follows. Section 6.7.2 of this SAP adopts the abbreviated categories from the eCRF.
  - Classic PMR-like symptoms, defined as shoulder and/or hip girdle pain associated with inflammatory morning stiffness
  - New or recurrent claudication in the peripheral circulation (i.e., in one of the extremities)

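### The SAP closes the TEAE window 90 days after the last SC dose; because a flare stops dosing, window length depends on the efficacy outcome, yet the tables compare only crude percentages.

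*SAP*

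**What the plan says.** - **TEAE definition.** Protocol 14.6.1, in defining TEAEs, sets a start and no end: "AEs that begin after the first administration of investigational products or existing AEs that worsen after the first dose of study medication are considered" as such. SAP 6.8.1 adds an end, "existing AEs that worsen after the first dose of study medication through the 90 days after the last dose date". That sentence could be read as limiting only worsening events, but SAP 7.1 settles it: "TEAE definition was updated to include AE through last dose + 90 days".
- **Which dose.** SAP 5.1.1: "Study drug or study treatment refers to SC KPL-301 or placebo". The prednisone taper does not extend the window.
- **Flare stops dosing.** The Protocol Synopsis (Base Treatment Period) and Sections 8.4.1, 10.3 and 11.2 make discontinuation of KPL-301 or placebo mandatory after a flare, in both arms.
- **Follow-up continues.** The Table 1 footnote on the EOT visit says that "subjects who discontinue treatment should continue attending their remaining scheduled visits for the duration of the study". Sections 8.4.1 and 11.2 agree. Protocol 13.4, however, ends AE collection 84 ± 3 days after the EOT visit.
- **Expected flares.** SAP 1.3 assumes that "the proportion of subjects without a flare by week 26 will be 50% in placebo and 85% in KPL-301".
- **Form of the tables.** SAP 6.8.1 plans numbers and percentages of subjects for TEAEs, TESAEs and TEAESIs. It plans no rate per person-time and no table with a common window. AEs beyond the limit appear only in listings.

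**The concern.** A window anchored to the last dose is harmless for a comparison between arms when stopping is unrelated to treatment. Here the main planned reason for stopping is the primary endpoint event, which the design expects in half of placebo subjects and in 15% of KPL-301 subjects. Someone who completes treatment is counted to about Week 37 or 38. Someone who flares is counted, on average, to about Week 23 or 24. The arm with more flares is counted for less time, so its crude percentage is lower even if the underlying AE rates are the same.

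Safety and tolerability is a stated secondary objective, and there are only about 42 and 28 subjects. A difference of a few points produced by window length could be read as a drug effect. Protocol 11.2 keeps early stoppers in safety follow-up specifically to deal with informative censoring, and the comparative tables as planned may not use all of that follow-up.

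**Working it through.** **Inputs.** Flare-free proportions at Week 26 of 50% and 85%, with exponential times (SAP 1.3); doses every 2 weeks (Protocol 9.5); window of 90/7 = 12.86 weeks after the last dose (SAP 6.8.1); study end at Week 38. SAP 6.6.4 has a category of exactly 14 injections, which suggests dosing from Day 0 to Week 26, so Week 26 is the base case and Week 24 the sensitivity case. The documents give no AE rates, so AE risks below are assumptions.

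**The plan's own figure.** Weekly flare hazards are −ln(0.50)/26 = 0.02666 on placebo and −ln(0.85)/26 = 0.00625 on KPL-301, a ratio of 0.234, with medians of 26 and 111 weeks. Power with 20 events at 3:2 is 87.3% by Freedman's formula and 88.8% by Schoenfeld's, which agrees with the stated 87%. Expected flares are 28 × 0.50 + 42 × 0.15 = 20.3.

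**Time to the earlier of flare or Week 26.** The mean is (1 − e^(−26λ))/λ. Placebo: 0.50/0.02666 = 18.8 weeks. KPL-301: 0.15/0.00625 = 24.0 weeks.

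**Window length.** Simulated, with last dose = last 2-weekly dose before the stop, and window end = the smaller of last dose + 12.86 and 38. Flaring subjects' windows close at mean Week 23.4 (placebo) and 24.5 (KPL-301). A completer with a last dose at Week 26 reaches 38.86, capped at 38. Hence:

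- Placebo: 0.50 × 38 + 0.50 × 23.4 = 30.7 weeks.
- KPL-301: 0.85 × 38 + 0.15 × 24.5 = 36.0 weeks.

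| Scenario | Gap (weeks) |
|---|---|
| 50% vs 85%, last planned dose Week 26 | 5.3 |
| 50% vs 85%, last planned dose Week 24 | 4.9 |
| 50% vs 85%, with 10–20% non-flare discontinuation (assumed) | 4.3–4.9 |
| 50% vs 70% | about 3 |
| 40% vs 85% | about 7 |
| No drug effect | 0 |

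**Effect on crude percentages.** Take the same constant AE hazard h in both arms, set so that 1 − e^(−38h) equals the assumed 38-week risk. The tabulated percentage is the mean of 1 − e^(−h × window).

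| Assumed 38-week risk | Placebo | KPL-301 | Artefact (points) |
|---|---|---|---|
| 10% | 8.1% | 9.5% | 1.4 |
| 20% | 16.4% | 19.0% | 2.6 |
| 50% | 42.1% | 47.8% | 5.7 |
| 80% | 70.5% | 77.4% | 6.9 |

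**Front-loaded AEs.** With a Weibull shape of 0.7 to 0.5 (assumed), the 5.7 points fall to 4.3–3.2, and the 2.6 points to 2.0–1.5.

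**Escape therapy.** Let the AE hazard after a flare be multiplied by 1.25, 1.5 or 2 (assumed). At a 50% baseline risk, the KPL-301 minus placebo difference inside the SAP window becomes +4.5, +3.4 or +1.2 points. Counted to Week 38 for everyone it becomes −2.0, −3.8 or −6.7.

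**The Protocol 13.4 reading.** If collection ends 84 days after an EOT visit held at the flare, mean collection ends at Week 18.8 + 12 = 30.8 on placebo and 24.0 + 12 = 36.0 on KPL-301, almost the same as the SAP window. If collection runs to Week 38, the window leaves out (38 − 30.7)/38, about 19%, of placebo follow-up and (38 − 36.0)/38, about 5%, of KPL-301 follow-up.

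**The case against.** **A drug-anchored window is a legitimate definition, and it is disclosed.** This stands. SAP 7.1 lists the change, and such a window answers a reasonable question about events near exposure. The difficulty is only that crude percentages are its sole between-arm summary.

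**A reader might infer that the tables are certain to be biased against KPL-301.** The documents do not support that. Relative to equal follow-up, truncation pushes against KPL-301 if the drug prevents flares. But subjects who flare may receive high-dose or IV corticosteroids or tocilizumab (Protocol 10.3), and the plan says nothing about AE rates afterwards. A doubled hazard nearly cancels the observed difference, and a larger increase could reverse it.

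**A reader might infer that late placebo events are recorded and then discarded.** That depends on Protocol 13.4. On one reading few such events would be collected at all, and the unequal observation would arise in collection as much as in the SAP. Any that are collected remain in the listings.

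**A reader might add the longer time on drug with KPL-301 (24.0 against 18.8 weeks) in the discontinuation and interruption tables.** That imbalance exists equally under Protocol 14.6.1 and does not come from the 90-day limit, so it does not support this point.

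**Making Week 38 the main window would bring in its own distortion.** This also stands: the added time is largely post-flare and falls mainly on placebo, which would tend to flatter KPL-301.

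**The effect is small against sampling error.** True. At the tabulated rates, the standard error of the difference is about 12 points for the 50% case and 9 for the 20% case. The artefact is, however, systematic, and it affects every TEAE, TESAE and TEAESI table in the same way.

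**Conclusion.** The point holds as a conditional one. The TEAE window ends at a time governed by the efficacy outcome, and the planned tables do not allow for unequal windows. At the design assumptions the gap is 4.9 to 5.3 weeks, depending on the last planned dose; it shrinks with a weaker drug effect and vanishes with none. With equal and constant AE hazards this adds roughly 1 to 7 points to the KPL-301 minus placebo difference across assumed risks of 10% to 80%, and less if AEs come early. The sign of the difference that will actually be observed is not determined by the documents. Safety summaries are descriptive, so no test or error rate is affected; what is at stake is how the harm comparison is read.

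**What to change.** 1. In SAP 6.8.1, keep the last dose + 90 days tables. Add to the TEAE, TESAE and TEAESI tables, by arm, the number of subjects with an event per person-time at risk, with time running to the first event or to the window end if there is none. With a constant hazard this removes the artefact: in the 50% example both arms give 1.8 per 100 person-weeks.
2. Add one supportive table counting AEs from first dose through Week 38, or study exit if earlier, for all treated subjects. Label it as including post-flare time on escape therapy, which falls mainly on placebo.
3. Reconcile Protocol 13.4 with Table 1 and Sections 8.4.1 and 11.2 on how long AEs are collected after early stopping. The supportive table depends on which applies; the person-time rates are usable either way.
4. Update the SAP 7.1 entry to match.

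**Cost.** SAP wording and extra runs of existing tables. Items 1 and 4 need no new data; item 2 needs none if AEs are collected to Week 38. Rates per person-time assume a roughly constant hazard. If AEs are front-loaded they tilt slightly the other way: with a Weibull shape of 0.7 and a 50% risk, 2.05 on placebo against 1.97 on KPL-301 per 100 person-weeks. They should therefore sit beside the crude percentages and not replace them.
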